10.3.2.2 The time-normalized number of HAE attacks requiring on-demand treatment

The secondary efficacy endpoint of time-normalized number of HAE attacks per month requiring on-demand treatment is calculated as:

$100 * [1 - (\text{number of HAE attacks requiring on-demand treatment during Treatment Period} / \text{length of subject treatment in days})] * 30.4375$

and annualized time-normalized number of HAE attacks requiring on-demand treatment is calculated as:

$100 * [1 - (\text{number of HAE attacks requiring on-demand treatment during Treatment Period} / \text{length of subject treatment in days})] * 365.25.$

Both will be summarized descriptively for the 6-month Treatment Period. Differences between the treatment arms will be tested in an exploratory manner via a two-sided Wilcoxon Test with alpha = 5%.

An HAE attack requiring on-demand treatment is defined as an attack for which the date of administration of an on-demand treatment is between the start (including) and end date (including) of a HAE attack.

Technical Note: Use answer for “On demand treatment taken?” from CRF form “HAE attack” to flag HAEs requiring on-demand treatment.

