10.3.2.4 Secondary Efficacy Analyses

The secondary efficacy endpoint of the percentage reduction in the time-normalized number of HAE attacks is calculated within a subject as:

$$100 * [1 - (\text{time-normalized number of HAE attacks per month during treatment} / \text{time-normalized number of HAE attacks per month during Run-in})]$$

for the entire 6-months of the Active Arm and for the 6-month Placebo Arm period and will be tested via a two-sided Wilcoxon Test using the individual percentage reduction between treatment groups.

The number and percentage of responders and non-responders will be presented with corresponding 95% CIs. A subject is classified as a responder if the percentage reduction in HAE attacks is $\geq 50\%$. In addition, the number and percentage of subjects with percentage reductions of $\geq 70\%$, and $\geq 90\%$ will be presented with corresponding 95% CIs.

The number and percentage of subjects with a percentage reduction of 100%, ie, who do not experience a HAE attack and so are attack-free, will be presented and summarized with corresponding 95% CI for the 6-month Active Arm period and for the 6-month Placebo Arm period, a Fisher-Test will be performed to assess for differences between treatments.

The percentage reduction in the time-normalized number of HAE attacks for the 6-months of the Active Arm will also be calculated as percentage reduction compared to the 6-month of the Placebo Arm (between subjects) as

$$100 * [1 - (\text{median time-normalized number of HAE attacks per month during 6 months of the Active Arm} / \text{median time-normalized number of HAE attacks per month during 6-months Placebo Arm period})]$$

and will be tested as exploratory via a two-sided Wilcoxon Test using the individual percentage reduction between treatment groups.

The secondary efficacy endpoint of time-normalized number of HAE attacks per month requiring on-demand treatment is calculated as:

$$100 * [1 - (\text{number of HAE attacks requiring on-demand treatment during treatment} / \text{length of subject treatment in days})] * 30.4375$$

An HAE attack requiring on-demand treatment is defined as an attack for which the date of administration of an on-demand treatment is between the start (including) and end date (including) of a HAE attack. Differences between the 6-months of the Active Arm and the 6-month Placebo Arm period will be tested in an exploratory manner via a two-sided Wilcoxon Test.

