For the analysis of the time-normalized number of moderate and/or severe HAE attacks, an analogue calculation will be done using all HAE attacks classified as moderate or severe.

The SGART will be presented descriptively. Comparison of the distribution of responses to therapy between CSL312 and placebo at the end of Treatment Period (Day 182) will be done.

To test for a difference in SGART between CSL312 and placebo, a comparison of the distribution of responses at the end of Treatment Period (Day 182) will be performed by using a two-sided Wilcoxon Test (alpha= 5%).

In addition, the secondary endpoints described above (except the SGART) will be summarized for the first 3 months (Day 1 to Day 91), as well as the second 3 months of the Active and Placebo Arms. Further, the following endpoints will be compared between the Active Arm and the Placebo Arm using the first 3 months (Day 1 to Day 91), as well as the second 3 months (Day 92 to Day 182) in an exploratory manner using the same tests as for the respective main analyses:

- Time-normalized number of HAE attacks per month.
- Percentage reduction in the time-normalized number of HAE attacks.
- Percentage of subjects with a percentage reduction of 100%.
- HAE attacks per month requiring on-demand treatment.

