4.1 Objectives and Endpoints

The primary objective of this study is to evaluate the efficacy of SC administration of CSL312 as prophylaxis to prevent HAE attacks in subjects with HAE.

Table 1 Primary Study Objective and Endpoint

Objective	Endpoint	Summary Measure(s)
Primary	Time-normalized number of hereditary angioedema (HAE) attacks during treatment from Day 1 through Day 182 ^a	The time-normalized number of HAE attacks (per month and annualized) in subjects treated once a month with either CSL312 (Active Arm) or placebo (Placebo Arm) during the period from Day 1 through Day 182 (6 months).

^aOnly investigator-confirmed HAE attacks based on the investigator's assessment of subject-reported symptoms will be included in the analysis of primary efficacy endpoint. Descriptions of confirmed HAE attack are provided in CSP Section 8.1.3 and CSP Appendix 2.

The secondary objectives of the study are:

1. To characterize the clinical efficacy of SC CSL312 in the prophylactic treatment of HAE.
2. To evaluate the safety of SC CSL312 in the prophylactic treatment of HAE.

Table 2 Secondary Study Objectives and Endpoints

Objective	Endpoint	Summary Measure(s)
Efficacy Endpoints		
1.	The reduction in the attack rate during the Treatment Period compared to the Run-in Period	The percentage reduction (at least $\geq 50\%$, $\geq 70\%$, ≥ 90 or equal to 100% [attack free]) in the time-normalized number of HAE attacks in subjects treated once a month with either CSL312 (Active Arm) or placebo (Placebo Arm) during the period from Day 1 through Day 182 (6 months) compared to the Run-in Period, as well as for the first 3-month time period and for the second 3-month time period of the Active and Placebo Arms compared to the Run-in Period.
1.	The time-normalized number of HAE attacks requiring on-demand treatment	The time-normalized number (per month and annualized) of HAE attacks requiring on-demand treatment in subjects treated once a month with either CSL312 (Active Arm) or placebo (Placebo Arm) during the period from Day 1 through Day 182 (6 months), as well as for the first 3-month time period and for the second 3-month time period of the Active and Placebo Arms.

Objective	Endpoint	Summary Measure(s)
Efficacy Endpoints		

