10.2 Subgroup Analyses

If ≥ 5 Japanese subjects are enrolled to the study, the following subgroup analysis will be carried out for Japanese and all subjects:

- Descriptive analysis of the primary endpoint: time-normalized number of HAE attacks per month during the Treatment Period, see [Section 10.1](#);
- Descriptive analysis of the reduction in attack rate during the Treatment Period, see [Section 10.3.2.1](#);
- Descriptive analysis of time-normalized number of HAE attacks requiring on-demand treatment, see [Section 10.3.2.2](#);
- Overview summary of TEAEs, see [Section 11.2](#);

If ≥ 5 Japanese subjects are enrolled to the study, the following subgroup analysis will be carried out for Japanese/non-Japanese subjects:

- Summary for CSL312 concentrations, see [Section 12.1](#).

Summaries for CSL312 concentrations will further be stratified by Age group (adolescent [12 to ≤ 17 years] and adult [>17 years] subjects), see [Section 12.1](#).

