10.3.2.3 The time-normalized number of moderate or severe HAE attacks

For the analysis of the time-normalized number of moderate or severe HAE attacks, an analogue calculation and analyses as described in [Section 10.3.2.2](#) will be done considering all HAE attacks classified as moderate or severe.

10.3.2.4 Time-normalized number of HAE attacks at various time points during the Treatment Period

The time-normalized number of HAE attacks (per month and annualized) during, the first 3-months Treatment Period and the second 3-months Treatment Period will be summarized descriptively and compared between the treatment arms using a two-sided Wilcoxon Test with alpha = 5%.

The time-normalized number of HAE attacks (per month) for the different Treatment Periods is calculated for a subject as:

[number of HAE attacks within first 3-months or second 3-months Treatment Period/ length of subject treatment in days] * 30.4375

and the time-normalized number of HAE attacks (annualized) as:

[number of HAE attacks within first 3-months or second 3-months Treatment Period/ length of subject treatment in days] * 30.4375

with length of subjects treatment in days derived as:

- First 3-months Treatment Period: [the date of Study Visit Day 91 or the End of Study date [whatever is first] – the date of Study Visit Day 1 of the Treatment Period +1];

- Second 3-months Treatment Period: [the date of Study Visit Day 182 or the End of Study date [whatever is first] – the date of Study Visit Day 91 of the Treatment Period].

Technical Note: A subject who discontinued in the first three months of Treatment Period will have a time-normalized number of HAE attacks for the first 3-months but not for the second 3-months Treatment Period.

The percentage reduction in the time-normalized number of HAE attacks for the Active Arm compared to the time-normalized number of HAE attacks for the Placebo Arm (between subjects) will be calculated as:

$$100 * [(mean \text{ time-normalized number of HAE attacks for CSL312} - mean \text{ time-normalized number of HAE attacks for Placebo}) / mean \text{ time-normalized number of HAE attacks for Placebo}]$$

[figure not shown]
and

$$100 * [(median \text{ time-normalized number of HAE attacks for CSL312} - median \text{ time-normalized number of HAE attacks for Placebo}) / median \text{ time-normalized number of HAE attacks for Placebo}].$$

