10.3.3 Supplementary Analyses of Secondary Endpoints

The secondary endpoints:

- percentage reduction in the time-normalized number of HAE attacks,
- number and percentage of subjects with percentage reductions of $\geq 50\%$, $\geq 70\%$, and $\geq 90\%$,
- time-normalized number of HAE attacks per month requiring on-demand treatment,
- the time-normalized number of moderate or severe HAE attacks,

(see [Section 10.3.2.1](#), [Section 10.3.2.2](#), [Section 10.3.2.3](#)) will be further summarized separately for the first 3 months Treatment Period (Study Day 1 to Day 91), as well as the second 3 months Treatment Period (Study Day 92 to Day 182).

Supplementary Analysis of Secondary Endpoints will be conducted for ITT Analysis Set.

[figure not shown]
HAE attacks

The number and percentage of mild, moderate, and severe HAE attacks will be presented as well as the time-normalized number of mild, moderate, and severe HAE attacks during Run-in Period and Treatment Period.

[figure not shown]
A by-subject listing will show all details per HAE attack sorted by treatment arm, subject-ID and HAE Attack ID including: nominal visit, start and end date:time, anatomical location, severity, on demand treatment taken, potential trigger for this HAE attack.

An additional listing will present absolute number and time-normalized number of all, mild, moderate, and severe HAE attacks per Run-in Period and Treatment Period, duration of Run-in Period and Treatment Period as used for time-normalization for each subject.

[figure not shown]
CCI

[figure not shown]
CCI

CCI

CCI

Time to first HAE attack after Day 1 and after Day 15 during Treatment Period

Time to first HAE attack after Study Day 1 and after Study Day 15 during Treatment Period will be analyzed using the Kaplan-Meier method. Time to first HAE attack after Day 1 will be derived as:

Date of first HAE attack after Study Day 1 – Date of Study Day 1,

and Time to first HAE attack after Day 15 will be derived as:

Date of first HAE attack after Study Day 15 – [Date of Study Day 1 + 14].

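### Programmed as printed, the on-demand and moderate/severe attack rates come out near 3,000 per month with direction reversed, and the annualised 3-month rate is 12 times too small

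*SAP*

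**What the plan says.** **On-demand rate.** SAP 4.1 (Table 2) describes the endpoint as "The time-normalized number (per month and annualized) of HAE attacks requiring on-demand treatment", which is a rate. SAP 10.3.2.2 then gives a formula that begins "100 * [1 - (\text{number of HAE attacks requiring on-demand treatment during Treatment Period", divides by the length of treatment in days, closes the bracket and multiplies by 30.4375. The annualised version is the same with 365.25. Protocol 10.3.2.4 has the monthly formula in the same form, beginning "100 * [1 - (\text{number of HAE attacks requiring on-demand treatment during treatment".

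**Moderate/severe rate.** Neither document writes a formula out. Protocol 10.3.2.4 says "an analogue calculation will be done using all HAE attacks classified as moderate or severe", and SAP 10.3.2.3 calls for "an analogue calculation and analyses as described in" SAP 10.3.2.2.

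**3-month all-attack rate.** SAP 10.3.2.4 gives attacks divided by days, times 30.4375, for the monthly value. It continues "and the time-normalized number of HAE attacks (annualized) as" and prints the identical expression, again ending in 30.4375.

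**Elsewhere in the SAP.** The primary endpoint in SAP 10.1 is attacks divided by days, times 30.4375 per month or 365.25 per year. SAP 8.2.2 gives the same month and year lengths. SAP section 5, which lists changes from the protocol, mentions none of these formulas.

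**The concern.** The wrapper of 100 times one minus a quantity belongs to the percentage reduction in SAP 10.3.2.1, where the inner term is a ratio of two rates. Here the inner term is attacks per day and the result is then scaled to a month. That is neither a rate nor a percentage, and it falls as attacks rise. In the 3-month section the yearly multiplier looks like a copy of the monthly one.

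If the text is followed, the summary tables for two named secondary efficacy endpoints would show uninterpretable values, with the better arm having the higher attack rate. The error would spread to the 3-month breakdowns of both endpoints, which SAP 10.3.3 says "will be further summarized separately for the first 3 months Treatment Period" and for the second. It would also reach the Japanese subgroup, where SAP 10.2 lists "Descriptive analysis of time-normalized number of HAE attacks requiring on-demand treatment" if at least 5 Japanese subjects are enrolled. The annualised 3-month table would simply repeat the monthly one.

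**Working it through.** **Inputs.** Treatment length L = 182 days, or 91 days for each 3-month period (SAP 10.1, 10.3.2.4). Month = 30.4375 days and year = 365.25 days (SAP 8.2.2). Planning rates are 0.3125 (CSL312) and 1.3 (placebo) attacks per month (Protocol 10.1, SAP 4.5). n is the number of qualifying attacks.

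**The plan's own figure.** The documents give no expected value for the affected endpoints. The one stated result built on the planning rates is power of about 90% with 24 and 16 subjects. The O'Brien-Castelloe approximation gives 90.7%, and 20,000 simulated trials give 91.6% with continuity correction and 91.9% without. The rates are therefore read as the plan intends.

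**Error 1: algebra.**

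100 × (1 − n/L) × 30.4375 = 3043.75 − 100 × [(n/L) × 30.4375]

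The printed monthly value is 3043.75 minus 100 times the true monthly rate. The printed yearly value is likewise 36,525 minus 100 times the true yearly rate.

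**Error 1: values.**

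| n | L | Printed, monthly | True, monthly | Printed, yearly | True, yearly |
|---|---|---|---|---|---|
| 0 | 182 | 3043.75 | 0 | 36,525 | 0 |
| 1 | 182 | 3027.03 | 0.17 | 36,324.3 | 2.01 |
| 8 | 182 | 2909.96 | 1.34 | 34,919.5 | 16.05 |
| 0 | 91 | 3043.75 | 0 | 36,525 | 0 |
| 4 | 91 | 2909.96 | 1.34 | 34,919.5 | 16.05 |

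**Error 1: arm means.** The documents do not say what share of attacks is treated on demand, so this step is an illustration. If every attack is treated:

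- CSL312: 3043.75 − 100 × 0.3125 = 3012.5
- Placebo: 3043.75 − 100 × 1.3 = 2913.75
- Printed contrast: 3012.5/2913.75 − 1 = +3.4%
- True contrast: 0.3125/1.3 − 1 = −76%

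With a treated share of 50% in both arms the printed means are 3028.13 and 2978.75 (+1.7%). With 25% they are 3035.94 and 3011.25 (+0.8%). The true contrast stays at −76%.

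**Error 2.** For 4 attacks in 91 days:

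- Printed yearly value: 4/91 × 30.4375 = 1.34
- Correct yearly value: 4/91 × 365.25 = 16.05
- Factor: 365.25/30.4375 = 12, whatever n and L are

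**Effect on tests.** Error 1 applies the same decreasing linear function to every subject's n/L. The ranks reverse and the two-sided Wilcoxon p-value is unchanged. In 2,000 simulated trials (36 CSL312, 24 placebo, 178 to 186 days of treatment) the largest p-value difference between printed and correct formulas was 0. Error 2 is a constant factor, so ranks and percentage reductions do not move.

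**The case against.** The strongest reply is that these are typographical slips whose intent nobody could mistake. Table 2 names the quantity as a rate, SAP 10.1 prints the correct form, and SAP 8.2.2 gives the conversions. A subject with no treated attacks and a rate above 3,000 per month would be caught at first output. The comparisons are exploratory and outside the testing hierarchy, and no p-value changes. SAP 10.3.3 also plans time-normalised numbers of mild, moderate and severe attacks and a per-subject listing with the durations used, so correct values could be recovered.

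Much of this stands. The intent is clear, the tests are safe, and nothing is lost from the data. The harm depends on literal programming. The +3.4% against −76% contrast shows the reversal but is not a planned table for these endpoints: the between-arm percentage reduction is specified for all attacks only.

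It does not remove the need for correction. SAP section 3 presents the document as a complete description and sends deviations to the study report, so quietly programming the right formula would be an undocumented departure. A second programmer working from the text would reproduce the error. The factor of 12 is the easier one to miss, because 1.34 is a plausible attack rate.

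**Conclusion.** Both errors are present in the current text and should be corrected before programming. As printed, the on-demand and moderate/severe rates run from 3043.75 downwards as attacks increase, so the arm with fewer attacks shows the higher value. The annualised 3-month all-attack rate is exactly 12 times too small.

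The per-subject values rest only on the printed formulas and the planned 182-day and 91-day periods. The arm means also assume that the all-attack planning rates apply and that the treated share is equal in the two arms. The moderate/severe part rests on the explicit cross-reference to SAP 10.3.2.2.

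The consequence is confined to estimates and their apparent direction. The primary endpoint and H01 to H04 do not use these formulas.

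**What to change.** - **Protocol 10.3.2.4 and SAP 10.3.2.2:** define the on-demand rate as (number of qualifying attacks / length of subject treatment in days) × 30.4375 per month and, in the SAP, × 365.25 per year. Delete the wrapper of 100 times one minus the quantity.
- **SAP 10.3.2.3 and the matching sentence in Protocol 10.3.2.4:** write the moderate/severe formula out in full instead of by analogy.
- **SAP 10.3.2.4:** replace 30.4375 with 365.25 in the annualised 3-month formula.
- **Outputs that depend on these:** check that the 3-month summaries in SAP 10.3.3, the Japanese subgroup summary in SAP 10.2 and the table shells follow the corrected definitions.

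The cost is a SAP text revision and an administrative correction to the protocol. Data collection, design, sample size and the testing hierarchy stay as they are.

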10.3.2.3 The time-normalized number of moderate or severe HAE attacks

For the analysis of the time-normalized number of moderate or severe HAE attacks, an analogue calculation and analyses as described in [Section 10.3.2.2](#) will be done considering all HAE attacks classified as moderate or severe.

10.3.2.4 Time-normalized number of HAE attacks at various time points during the Treatment Period

The time-normalized number of HAE attacks (per month and annualized) during, the first 3-months Treatment Period and the second 3-months Treatment Period will be summarized descriptively and compared between the treatment arms using a two-sided Wilcoxon Test with alpha = 5%.

The time-normalized number of HAE attacks (per month) for the different Treatment Periods is calculated for a subject as:

[number of HAE attacks within first 3-months or second 3-months Treatment Period/ length of subject treatment in days] * 30.4375

and the time-normalized number of HAE attacks (annualized) as:

[number of HAE attacks within first 3-months or second 3-months Treatment Period/ length of subject treatment in days] * 30.4375

with length of subjects treatment in days derived as:

- First 3-months Treatment Period: [the date of Study Visit Day 91 or the End of Study date [whatever is first] – the date of Study Visit Day 1 of the Treatment Period +1];

- Second 3-months Treatment Period: [the date of Study Visit Day 182 or the End of Study date [whatever is first] – the date of Study Visit Day 91 of the Treatment Period].

Technical Note: A subject who discontinued in the first three months of Treatment Period will have a time-normalized number of HAE attacks for the first 3-months but not for the second 3-months Treatment Period.

The percentage reduction in the time-normalized number of HAE attacks for the Active Arm compared to the time-normalized number of HAE attacks for the Placebo Arm (between subjects) will be calculated as:

$$100 * [(mean \text{ time-normalized number of HAE attacks for CSL312} - mean \text{ time-normalized number of HAE attacks for Placebo}) / mean \text{ time-normalized number of HAE attacks for Placebo}]$$

[figure not shown]
and

$$100 * [(median \text{ time-normalized number of HAE attacks for CSL312} - median \text{ time-normalized number of HAE attacks for Placebo}) / median \text{ time-normalized number of HAE attacks for Placebo}].$$

The 95% two-sided Confidence Intervals for the relative difference in means and medians will be calculated by using the estimated upper and lower confidence limits for the corresponding time-normalized number of HAE attacks ratio, transform by subtracting 1 and multiplying by 100% [Beyene & Moinedding, 2005, Price & Bonett, 2010].

The percentage reduction will be calculated for the time-normalized number of HAE attacks between the Active Arm and the Placebo Arm for the 6-month Treatment Period (Hierarchical Testing H02), as well as for the first 3 months and the second 3 months of the Treatment Period.

CCI

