4.5 Determination of the Sample Size

In total, 60 subjects are planned to be randomized.

Forty subjects with C1-INH HAE type 1 and type 2 completing the 6-month Treatment Period are needed to achieve a power of approximately 90% for a two-sided Wilcoxon Test (alpha of 5%). Subjects will be randomized to the Active Arm or the Placebo Arm with a ratio of 3:2. An attack rate per month of 0.3125 for CSL312-treated subjects and of 1.3 for subjects receiving placebo are assumed. The monthly attack rates of placebo and of CSL312 are assumed to be Poisson distributed.

The sample size calculation is performed with SAS 9.4 using proc power procedure with twosamplewilcoxon test=WMW which performs power analyses for the Wilcoxon-Test for two independent groups, i.e. the CSL312 and the Placebo treatment in Study CSL312_3001. The Wilcoxon Rank Sum test is testing from departure from the null hypothesis and is assessing if there is a location shift between the distributions of the HAE attack rates of the CSL312 and the Placebo treatment. SAS Proc Power procedure uses the O'Brien-Castelloe approach to compute approximate power. Alpha is set to 5% [O'Brien & Castelloe, 2006]. The assumed monthly attack rates of placebo and of CSL312 (i.e. 1.3 and 0.3125 attacks/month, respectively) are used as the two means of the two Poisson distributions. The randomization ratio of 3:2 was implemented by GROUPNS = (24 16) resulting in a total sample size of 40 which is the lowest one reaching 90% power.

It is targeted to randomize approximately 5 adolescents into the treatment period with a randomization ratio of 3:2 (active:placebo).

To allow for sufficient safety data, to increase the likelihood of adolescents entering the study and, to have at least 40 subjects reaching the end of the study, an additional 20 subjects are planned to be randomized.

In case it is not feasible to randomize the targeted number of adolescents, the targeted total sample size will be achieved by randomizing the needed number with adult subjects.

In addition, it is targeted to include 5 Japanese subjects into the total 60 subjects randomized.

Based on Method 1 and Method 2 in the [Basic principles on Global Clinical Trials] the sample size of the Japanese subjects are planned as below. The point estimate of the endpoint in each arm for Japanese population and other regions (for Method 2) are assumed as the same as that for the global population.

Method 1

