With setting the notations of treatment differences between CSL312 and placebo arm as D, the treatment difference in the global population as D_{all} , and the treatment difference in the Japanese subpopulation as D_{Japan} , the probabilities of $D_{Japan}/ D_{all} > 0.5$ were calculated for the settings that the global sample size is 60 patients (CSL312 arm = 36 patients, and placebo arm = 24 patients) including the Japanese sample size of 5 – 8. The Japanese sample sizes of each arm were rounded based on the 3:2 randomization ratio.

Table 4 Sample Size Justification for Japanese Subjects - Method 1

Japanese sample size			Probability (%) of $D_{Japan}/ D_{all} > 0.5$	
Total	CSL312	Placebo	With median	With mean
5	3	2	64	70
6	4	2	63	71
7	4	3	65	76
8	5	3	73	76

Method 2

With setting the notations of treatment differences between CSL312 and placebo arm as D, the treatment difference in the global population as D_{all} , the treatment difference in the Japanese subpopulation as D_{Japan} and the treatment difference in other regions x as $D_{other-x}$, the probabilities of that all of the global, Japan and other regions of $D > 0$ were calculated for the settings that the global sample size is 60 patients (CSL312 arm = 36 patients, and placebo arm = 24 patients), the Japanese sample size is 5 – 8, the sample size of North America and Europe are assumed to be the same. The sample sizes of each arm for Japan and other regions were rounded up based on 3:2 randomization ratio.

Table 5 Sample Size Justification for Japanese Subjects - Method 2

Sample size for each region			Probability (%) of all of D >0	
Japan	North America*	Europe*	With median	With mean
5	27	28	75	86
6	27	27	73	85
7	26	27	70	91
8	26	26	67	92

* Expected that the sample sizes for North America and Europe would be the same. If not divisible, the sample size of Europe includes one more patients than that of North America.

As the results, if the Japanese sample size is 8, the probabilities to achieve consistency between the Japanese subset and the global population are 67%–92% using mean and median with 3:2 randomization ratio based on Method 1 and 2. Eighty percent probability would be achieved with 5 Japanese patients already when using the mean and Method 2.

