$$[\text{the number of HAE attacks} / \text{length of subject treatment in days}] * 365.25.$$

The time-normalized number of HAE attacks will not be calculated if the subject's observation time for the Treatment Period is less than 30 days, i.e. subject discontinued within 30 days after first study drug administration.

The randomization is stratified by the variables age (≤ 17 years, > 17 years) and, for adults, the subject's baseline attack rate (1 to < 3 attacks/month, and ≥ 3 attacks/month) during the Run-in period. Age and baseline attack rate are not regarded as confounder or effect modifier. The stratification by age is implemented to mitigate the risk that adolescent subjects could be randomized all to the same treatment, with worst case scenario that all adolescents are on placebo treatment. There is no significant physiological basis to suggest different efficacy or safety profiles in adults and adolescents and the distribution of attack locations in adolescent subjects typically mirrors that of adults [[MacGinnitie, 2014](#)].

It is expected that around 50% of subjects will have 1 to < 3 attacks/month and around 50% of subjects will have ≥ 3 attacks/month as baseline attack rate [[Banerji, 2018](#)]. Because of the stratified randomization these two subgroups of subjects will be equally distributed to the Active and to the Placebo arm. It is assumed that the treatment effect, i.e. the time-normalized number of HAE attacks observed under CSL312 treatment, is not impacted by the baseline attack rate. Nevertheless, the time-normalized number of HAE attacks will be compared for

the 6 months of the Active Arm and the 6 months of Placebo Arm using a Poisson Regression model including baseline attack rate as fixed effect in a sensitivity analysis, see [Section 10.1.2](#).

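### SAP 10.3.2.4 sets no minimum length for the second 3-month period, so one subject who leaves soon after Visit Day 91 can distort the exploratory mean-based reduction for that period.

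*SAP*

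**What the plan says.** SAP 10.3.2.4 defines a subject-level rate for each half of the Treatment Period. The first half runs from Day 1 to the earlier of the Visit Day 91 date and the End of Study date. The length of the second half begins "Second 3-months Treatment Period: [the date of Study Visit Day 182 or the End of Study date [whatever is first", and the Visit Day 91 date is subtracted. No minimum is given. The same section plans a between-arm percentage reduction in means and another in medians, and SAP 10.3.2.4 adds confidence intervals and applies both to each 3-month period as well as to the full six months.

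For the full period, SAP 10.1 calculates no rate if the "observation time for the Treatment Period is less than 30 days". SAP 8.1 gives the reasoning: phase 2 data are taken to show that rates observed over more than 30 days and less than 6 months are comparable with 6-month rates. It carries that assumption to the secondary endpoints based on attack rate.

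The Technical Note in SAP 10.3.2.4 says: "A subject who discontinued in the first three months of Treatment Period will have a time-normalized number of HAE attacks for the first 3-months". It adds that such a subject has no second-period rate, and it does not mention the 30-day rule.

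On the boundary, SAP 10.3.2.4 uses the actual visit date, which may fall 4 days either side of Day 91 (protocol 8.7.1). SAP 10.3.3 summarizes other secondary endpoints "separately for the first 3 months Treatment Period (Study Day 1 to Day 91") and Study Day 92 to 182. Protocol 10.3.2.4 uses those same fixed days for the attack rate itself. SAP 10.3.2.1, which contains the H03 test, speaks only of the first 3 months after first dosing.

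**The concern.** The SAP's case for treating a short rate as equivalent to a full one rests on more than 30 days of observation. The second-period formula can breach that premise for a subject who satisfies the whole-period rule. A subject leaving on Study Day 95 after a visit on Day 91 has 95 days of treatment-period observation but 4 days in the second period.

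The arm mean gives every subject equal weight, however briefly observed. One attack over a very short denominator can therefore dominate it. What is at stake is the reported second-period percentage reduction in means and its confidence interval, which readers will use to judge whether the effect lasts.

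**Working it through.** **Inputs from the SAP.** Planning rates (4.5): "An attack rate per month of 0.3125 for CSL312-treated subjects and of 1.3 for subjects receiving placebo are assumed". Randomized arms (4.5): "CSL312 arm = 36 patients, and placebo arm = 24 patients". Days per month (8.2.2): 30.4375.

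**Assumption.** The documents do not say when subjects leave or how many attacks they have. I take one leaver with one attack in d days of the second period, and put every other subject at the planning rate.

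**The plan's own figure.** The SAP says 40 completers "are needed to achieve a power of approximately 90% for a two-sided Wilcoxon Test (alpha of 5"%), and that "The randomization ratio of 3:2 was implemented by GROUPNS = (24 16) resulting in a total sample size of 40". The O'Brien-Castelloe method with Poisson means 0.3125 and 1.3 gives a Wilcoxon-Mann-Whitney odds of 3.30 and power of 0.907 at 24 and 16 (0.893 at 23 and 15). Simulation at 24 and 16 gave 0.914. The planning figure is reproduced.

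**Base reduction.** 1 − 0.3125/1.3 = 76.0%. The SAP formula carries a minus sign; I show reductions as positive.

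**One leaver, one attack in 4 days.** Rate = (1/4) × 30.4375 = 7.61 per month.
- CSL312 leaver: mean = (35 × 0.3125 + 7.61)/36 = 0.515; reduction = 1 − 0.515/1.3 = 60.4%.
- Placebo leaver: mean = (23 × 1.3 + 7.61)/24 = 1.563; reduction = 1 − 0.3125/1.563 = 80.0%.
- CSL312 leaver with only 24 and 16 subjects: mean = (23 × 0.3125 + 7.61)/24 = 0.617; reduction = 52.6%.

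**Dependence on d (CSL312 leaver, 36 and 24).**

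| Days in second period | Rate per month | Reduction | Shift (points) |
|---|---|---|---|
| 2 | 15.22 | 44.1% | −31.9 |
| 5 | 6.09 | 63.6% | −12.3 |
| 7 | 4.35 | 67.3% | −8.6 |
| 14 | 2.17 | 72.0% | −4.0 |
| 30 | 1.01 | 74.5% | −1.5 |

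**Chance of at least one attack in 4 days.** CSL312: 1 − exp(−0.3125 × 4/30.4375) = 4.0%. Placebo: 1 − exp(−1.3 × 4/30.4375) = 15.7%. A leaver with no attack moves the reduction by +0.7 points (CSL312) or −1.0 (placebo).

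**Robust summaries.** In simulations with 91-day Poisson counts and one CSL312 leaver with one attack in 2 days, the median-based reduction was unchanged in 95% of runs. Its average shift was −0.7 points and the largest in any run was 25. Power of the 3-month Wilcoxon test stayed at about 100% with or without the leaver.

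**Boundary alone.** A visit on Day 87 instead of 91 changes a subject's first-period rate by 91/87 − 1 = 4.6%; a visit on Day 95 changes it by 91/95 − 1 = −4.2%. Moving one CSL312 attack across the boundary changes the arm mean by (30.4375/91)/36 = 0.0093, which is 0.0093/1.3 = 0.7 points of reduction.

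**After the fix.** With a 30-day minimum, one attack in 30 days moves the reduction by 1.5 points. Three attacks in 30 days (3.04 per month) still move it by 5.8. With total attacks over total time, one attack in 4 days gives a CSL312 rate of (35 × 0.3125 × 91/30.4375 + 1)/((35 × 91 + 4)/30.4375) = 0.322 and a reduction of 75.3%, a shift of 0.7 points.

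**The case against.** The best defence is that the case is uncommon and the damage contained. The subject must withdraw from the study, not merely stop the drug, within days of a dosing visit, and must also have an attack in those days. Protocol 4.3.1 and 4.3.2 encourage subjects who stop treatment to stay until Day 182. SAP 10.3.2.4 also plans a median-based reduction, and SAP 10.5 makes the 3-month rate comparisons exploratory. All of this stands and limits the importance of the point. It does not remove the gap, because the mean-based figure will still be reported for each period.

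Four stronger readings are tempting, and the documents do not support them.

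- A reader might infer that the first period has no minimum either. SAP 8.1 and 10.1 already make the rate missing for subjects who leave within 30 days of first dosing. The Technical Note omits that exception but does not claim to override it, so the two texts need aligning.
- A reader might infer a division by zero when the End of Study date is the Visit Day 91 date. Such a subject has probably left in the first three months under the Technical Note, and so has no second-period rate.
- A reader might blame the Day 91 boundary conflict for the large shifts. It accounts for under one point per CSL312 attack moved; the missing minimum accounts for the rest.
- A reader might extend the concern to the confirmatory results. H01 and H02 use 6-month rates, which have the 30-day rule. H03 counts attack-free subjects and has no time denominator, so only the boundary definition matters there.

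**Conclusion.** The point holds for the second 3-month period. A CSL312 leaver with one attack in 4 days takes the mean-based reduction from 76.0% to 60.4%, and a placebo leaver takes it to 80.0%. The shift grows for shorter stays and falls to 1.5 points by 30 days for one attack on CSL312. These figures assume planning rates for all other subjects, arms of 36 and 24, and a single such leaver; how often such withdrawals occur is unknown from the documents. The estimate affected is exploratory, so this is a minor but worthwhile correction.

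The first-period Technical Note and the Day 91 boundary are matters of consistency, with small numerical effect.

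**What to change.** 1. In SAP 10.3.2.4, require at least 30 days of observation within the second 3-month period before calculating a subject-level rate. Alternatively, report the mean-based 3-month reduction as total attacks over total time, which keeps every observed attack.
2. State in the Technical Note that the 30-day rule applies to the first-period rate.
3. Use one boundary, Study Day 91/92, for both attack counts and days in SAP 10.3.2.1 (including H03), 10.3.2.4 and 10.3.3. This matches protocol 10.3.2.4 and does not depend on the Day 91 visit having taken place.

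The cost is a few sentences in the SAP. With the 30-day minimum, a few subjects have no second-period rate and their few days of second-period data drop out of that summary. A subject with several attacks in just over 30 days could still move the mean by several points. The total-over-total alternative avoids the exclusions but weights subjects by time observed, so it should be labelled as a different summary from the mean of individual rates.
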